5.1.4. Visit Windows

For the extension visits, visit based assessments are generally summarized according to the nominal visit, except for subjects prematurely discontinuing study treatment, which are re-assigned following the visit windowing described in Section 5.1.10. Scheduled nominal visits, e.g., Week XX, are identified based on the eCRF recorded nominal visit label. Note that the eCRF allows for considering a visit under multiple visit labels, e.g., a Follow-up 1 or a Relapse visit can be considered in addition a Week XX visit. This second visit label is collected on the Visit Summary eCRF under 'Corresponding visit'. In selecting results for a nominal scheduled visit both visit labels are considered. Priority is given to the first visit label, then to the second visit label. If no result is available at a scheduled nominal visit, premature EOT remapping is applied [Section 5.1.10].

In addition, to incorporate the extended 288-week treatment period for Ukraine subjects impacted by regional crisis, additional visits (Extension Visit 24, Visit 25, Visit 26, Visit 27) will be added. The Extension Visit 23-Week 240 contains data from regional crisis-impacted Ukraine subjects who attend this visit, as well as the Extension EOT visit data of other non-impacted subjects who complete study treatment until week 240. The Extension EOT visit contains Visit 27- Week 288 visit data from regional crisis-impacted Ukraine subjects, as well as the Extension EOT visit data of other non-impacted subjects (including subjects who completed study treatment at Week 240 and subjects who switched to commercial ponesimod at early weeks and subjects who discontinued study treatment prematurely at earlier weeks).

Extension Analysis Period

Summaries by visit are presented by extension baseline (derived), and further scheduled nominal visits up to Week 240 (or up to Week 288 for Ukraine subjects). Generally, by-visit tables tabulate the extension baseline and nominal and derived visits as follows:

- Extension baseline (Note: This is not a nominal visit but the derived baseline [see Section 5.1.3.1])
- Extension Visit 2 Week 2
- Extension Visit 3 Week 4
- Extension Visit 4 Week 12
- Extension Visit 5 Week 24
- Extension Visit 6 Week 36
- Extension Visit 7 Week 48
- Extension Visit 8 Week 60
- Extension Visit 9 Week 72
- Extension Visit 10 Week 84
- Extension Visit 11 Week 96
- Extension Visit 12 Week 108
- Extension Visit 13 Week 120
- Extension Visit 14 Week 132
- Extension Visit 15 Week 144
- Extension Visit 16 Week 156
- Extension Visit 17 Week 168
- Extension Visit 18 Week 180
- Extension Visit 19 Week 192
- Extension Visit 20 Week 204
- Extension Visit 21 Week 216
- Extension Visit 22 Week 228
- Extension Visit 23 Week 240
- Extension Visit 24 Week 252 (This is applicable for Ukraine subjects only)
- Extension Visit 25 Week 264 (This is applicable for Ukraine subjects only)
- Extension Visit 26 Week 276 (This is applicable for Ukraine subjects only)
- Extension Visit 27 Week 288 (This is applicable for Ukraine subjects only)
- Extension EOT Visit
- Extension EOS Visit

Premature EOT visits and EOT visits from subjects who switched to commercial ponesimod are mapped to and summarized within a scheduled visit, following the window approach described in Section 5.1.10; they will not be summarized as "Visit 23 - Week 240" (or "Visit 27 – Week 288, for impacted Ukraine subjects) unless they are mapped to this visit using the approach described in Section 5.1.10.

Combined Analysis Period

Summaries by visit are presented by Core Baseline (derived), and further scheduled nominal core visits up to Core Week 108, derived Follow-up visits (FU1, FU2), Extension Baseline and further scheduled nominal extension visits up to Extension Week 240 (or Extension Week 288, for impacted Ukraine subjects). Generally, by visit tables tabulate the baselines and nominal and derived visits as follows:

- Core Baseline (Note: This is not a nominal visit but the derived baseline, see Section 5.5.1 of the core CSR SAP)
- Core Visit 4 Week 2
- Core Visit 5 Week 4
- Core Visit 6 Week 12
- Core Visit 7 Week 24
- Core Visit 8 Week 36
- Core Visit 9 Week 48
- Core Visit 10 Week 60
- Core Visit 11 Week 72
- Core Visit 12 Week 84
- Core Visit 13 Week 96
- Core Visit 14 Week 108
- Core Day-15 follow-up (derived)
- Core Day-30 follow-up (derived)
- Extension baseline (Note: This is not a nominal visit but the derived baseline for the extension study [see Section 5.1.3.1])
- Extension Visit 2 Week 2
- Extension Visit 3 Week 4
- Extension Visit 4 Week 12
- Extension Visit 5 Week 24
- Extension Visit 6 Week 36
- Extension Visit 7 Week 48
- Extension Visit 8 Week 60
- Extension Visit 9 Week 72
- Extension Visit 10 Week 84
- Extension Visit 11 Week 96
- Extension Visit 12 Week 108
- Extension Visit 13 Week 120
- Extension Visit 14 Week 132
- Extension Visit 15 Week 144
- Extension Visit 16 Week 156
- Extension Visit 17 Week 168

- Extension Visit 18 Week 180
- Extension Visit 19 Week 192
- Extension Visit 20 Week 204
- Extension Visit 21 Week 216
- Extension Visit 22 Week 228
- Extension Visit 23 Week 240
- Extension Visit 24 Week 252 (This is applicable for Ukraine subjects only)
- Extension Visit 25 Week 264 (This is applicable for Ukraine subjects only)
- Extension Visit 26 Week 276 (This is applicable for Ukraine subjects only)
- Extension Visit 27 Week 288 (This is applicable for Ukraine subjects only)
- Extension EOT Visit
- Extension EOS Visit.

5.1.5. Analysis Strategy

5.1.5.1. Analysis strategy for efficacy

In order to describe the disease activity in subjects after long-term treatment with ponesimod 20 mg, and to investigate the effect of switching from teriflunomide 14 mg to ponesimod 20 mg, the main analysis of efficacy will focus on combined data from both the core and extension studies. Subjects will be analyzed according to the treatment they were randomized to in the core study (the randomized treatment variable from the core study ADaMs will be used). This will allow the assessment of the effect of early long-term treatment with ponesimod 20 mg compared with delaying the treatment with ponesimod 20 mg for 2 years.

Following 108 weeks of treatment with either ponesimod 20 mg or teriflunomide 14 mg in the core study, it must be assumed that the two populations will not be similar in terms of baseline characteristics at the start of the extension study. With this limitation acknowledged, specific efficacy endpoints will be analyzed only for the extension study, split by core study randomized treatment and overall. Section 4.2 details which efficacy endpoints will be analyzed for the combined core and extension studies, which additionally will be analyzed for the extension study, and which will be analyzed for the core study.

5.1.5.2. Analysis strategy for safety

The long-term safety of ponesimod and the changes in safety in teriflunomide 14 mg subjects switching to ponesimod 20 mg will be investigated by summarizing the combined data from both the core and extension studies. Subjects will be analyzed according to the actual treatment they received in the core study (as derived in the core study ADaMs and not re-derived for the extension study analysis). Cumulative data such as AEs and SAEs will only be summarized for subjects initially treated with ponesimod 20 mg in the core study to allow a long-term assessment of up to 6 years. To assess trends over time and to assess the switch from teriflunomide 14 mg to ponesimod 20 mg, the analysis of the change from baseline for safety endpoints will be assessed by core study treatment group and by visit from core baseline up to last treatment + 15 days plus the EOS visit.

In addition, all safety data collected in the extension study will be analyzed for the extension study only and will summarize both overall and split by the core study treatment group. For this analysis, the extension study baseline is used as the reference.

5.1.6. Definition of treatment-emergent

A safety assessment (ECG, vital signs, laboratory, etc.) is considered treatment-emergent relative to the Analysis Period, and a safety event (AE, serious adverse event [SAE], Death, etc.) is considered treatment-emergent relative to the Analysis Period, if the assessment date is on or after the study treatment start date in the Analysis Period and prior to or on the study treatment end date + 15 days (inclusive). In case of planned pregnancy interruption, a safety assessment is considered treatment emergent relative to the Analysis Period if one of the following conditions is met:

- the assessment date is on or after the study treatment start date in the Analysis Period and prior to or on the last study drug intake date prior to pregnancy interruption + 15 days (inclusive)
- the assessment date is on or after the re-initiation date of study treatment after planned pregnancy and prior to or on the End of Treatment (EOT) date + 15 days (inclusive).

In case of multiple planned pregnancies interruptions, the above definition will be adapted, that any assessment in the following interval is not considered as treatment emergent: date between the last study drug intake date prior to each pregnancy interruption + 15 days (inclusive) and the reinitiation date of study treatment after each planned pregnancy (excluded).

If both the assessment date/time and the date/time of study treatment start (or of re initiation after planned pregnancy) are available, only events with date/time on or after the date/time of study treatment start (or of re initiation after planned pregnancy) are considered to be treatment emergent. In case of (partially) missing assessment dates/times, or for assessments on treatment Day 1 with reported assessment time contradicting the time point label, the nominal visit and time point labels will be used to determine whether an assessment is considered as treatment-emergent or not. For example, a blood pressure measurement with an assessment date on Day 1 but a missing assessment time or an assessment time after the time of first study drug intake, will not be considered treatment emergent if reported under the time point "Pre-dose" in the eCRF, however it will be considered treatment-emergent if reported as "2 hours post-dose" in the eCRF.

Missing or partially missing onset or occurrence dates are imputed as described in Section 6.13. If both the onset/occurrence date/time and the date/time of study treatment start are available, only events with date/time on or after the date/time of study treatment start are considered to be treatment emergent.

For subjects who are currently on an interruption for planned pregnancy on the database lock date, study treatment end date for the above definitions is taken as the date associated with the study drug record on the "Maintenance" eCRF page of the extension study, where reason for treatment end = "Temporarily interrupted due to planned pregnancy as defined in the protocol".

5.1.7. Study Day

5.1.7.1. Extension Study Day

For all data analyses on the Extension Analysis Period described in this SAP, the first day of study drug intake in the extension study is defined as Extension study Day 1. The day prior to study drug start date in the extension study is defined as Extension study Day minus 1; therefore there is no study Day 0. Study days of dates prior to Extension Day 1 are calculated as 'date minus extension

study drug start date', and study days of date after Extension Day 1 are calculated as 'date minus extension study drug start date + 1'.

5.1.7.2. Combined Study Day

For all data analyses on the Combined Analysis Period Study, **Day** refers to the number of days elapsed since randomization date plus 1 (e.g., Combined Study Day 1 is the day of randomization). For dates prior to randomization, the combined study day is the negative number of days elapsed between the date under consideration and the day of randomization. Therefore, there is no study Day 0.

5.1.8. Coding

The following coding dictionaries will be used:

- AEs will be coded using MedDRA version 26.0;
- Medications (previous and concomitant) will be coded using the WHO-Drug Dictionary version March 2023 B3G.

5.1.9. Dates

The following variables for the core study are used as derived in the core study, and are not rederived for the extension analysis:

- Core study treatment start date;
- Core EOT / study treatment end date;
- Core EOS date;
- Core screening date;
- Core Study Day;
- Core Treatment Day.

5.1.9.1. Extension enrollment date

The extension enrollment date is the date when the subject signed the Informed Consent Form and is taken directly from RAVE.

5.1.9.2. First study drug intake date/time in extension study

The first study drug intake date/time in the extension study is taken as the earliest intake documented in any of the following eCRF sections: 'Study Drug Administration - Day 1 / Re-Initiation', 'Study Drug Administration', Study drug administration - Re-initiation after planned pregnancy', 'Up-titration Summary', 'Up-titration Ponesimod', or 'Maintenance Ponesimod'. This is derived in the SDTM.DM dataset as the 'Date/Time of first study treatment' (RFXSTDTC).

5.1.9.3. Extension End-of-Treatment (EOT) date

If a subject is considered to have prematurely discontinued treatment in the extension study, the date of last study drug intake in the extension study corresponds the end of treatment date, derived as:

• The maximum of [End date up-titration on eCRF page 'Up-titration Summary', Treatment end date on eCRF page 'Up-titration Ponesimod'; Treatment end date on eCRF page 'Maintenance

- Ponesimod']; this is derived in the SDTM.DM dataset as the 'Date/Time of last study treatment' (RFXENDTC);
- If missing based on the above, then the treatment termination date as recorded on the RAVE primary form is taken. This is derived in the SDTM.DS dataset as 'Start Date/Time of Disposition Event' (DSSTDTC) where the 'Subcategory for Disposition Event' (DSSCAT) is 'TREATMENT TERMINATION' and the 'Standardized Disposition Term' (DSDECOD) is not 'COMPLETED'.

If a subject is considered to have completed treatment as per protocol, the date of last extension study drug intake corresponds to the minimum of:

- Treatment end date on extension study eCRF page 'Maintenance Ponesimod' corresponding to the record "Completed as per protocol"; this is derived in the SDTM.DM dataset as the 'Date/Time of last study treatment' (RFXENDTC);
- If missing based on the above, then the treatment termination date as recorded on the RAVE primary form is taken. This is derived in the SDTM.DS dataset as 'Start Date/Time of Disposition Event' (DSSTDTC) where the 'Subcategory for Disposition Event' (DSSCAT) is 'TREATMENT TERMINATION' and the 'Standardized Disposition Term' (DSDECOD) is 'COMPLETED';

5.1.9.4. Extension End-of-Study (EOS) date

If a subject is considered to have completed the extension study per protocol, the extension End-of-Study (EOS) date is defined as the date on the end of extension study eCRF page. This is derived in the SDTM.DM dataset as the 'Subject Reference End Date/Time' (RFENDTC). If this date is missing, the last recorded visit on the eCRF is considered as the extension EOS date. If this date is also missing, the date of last contact during the extension study is taken, derived in the SDTM.DS dataset as 'Start Date/Time of Disposition Event' (DSSTDTC) where the 'Standardized Disposition Term' (DSDECOD) is not 'LOST TO FOLLOW-UP'.

5.1.10. Re-assignment of EOT visits / visit windowing

For core study, analysis visits are used as derived in the core study and are not re-derived for the extension analysis.

Extension study

If a subject discontinued study drug prematurely, as defined in Section 5.4.1.1.5, the EOT visit will be considered as the premature EOT visit. This rule also applies to subjects who are treatment completers but switched to commercial ponesimod prior to Week 240.

For all parameters unless stated below: For subjects who discontinued study drug prematurely with available premature EOT visit and subjects who switched to commercial ponesimod, the visit may be re-assigned to a scheduled visit as follows:

• If a result is missing for a scheduled visit, it can be replaced with a result from a premature EOT visit available in the respective visit window [see Table 7].

Table 7: Premature End-of-Treatment remapping

Visit window	Nominal value Day	Lower limit for Day	Upper limit for Day
Week 2	15	2	22
Week 4 (Except LB)	29	23	70
Week 12 (Except LB)	85	71	126
Week 4* (For LB only)	29	23	42
Week 8* (For LB only)	57	43	70
Week 12* (For LB only)	85	71	98
Week 16* (For LB only)	113	99	126
Week 20* (For LB only)	141	127	154
Week 24* (For LB only)	169	155	210
Week 24 (Except LB)	169	127	210
Week 36	253	211	294
Week 48	337	295	378
Week 60	421	379	462
Week 72	505	463	546
Week 84	589	547	630
Week 96	673	631	714
Week 108	757	715	798
Week 120	841	799	882
Week 132	925	883	966
Week 144	1009	967	1050
Week 156	1093	1051	1134
Week 168	1177	1135	1218
Week 180	1261	1219	1302
Week 192	1345	1303	1386
Week 204	1429	1387	1470
Week 216	1513	1471	1554
Week 228	1597	1555	1638
Week 240	1681	1639	Open end** / 1722***
Week 252***	1765	1723	1806
Week 264***	1849	1807	1890
Week 276***	1933	1891	1974
Week 288***	2017	1975	Open end

Day refers to treatment day, i.e., days from extension study treatment start.

MRI and C-SSRS: For MRI and C-SSRS measurements visit windowing of premature EOT visits is conducted using \pm 3 months around the target day (Week 48: Day 246 to Day 428; Week 96: Day 582 to Day 764; Week 144: Day 918 to Day 1100; Week 192: Day 1254 to Day 1436; Week 240: \geq Day 1590 for subjects who are not impacted by extended study duration, or Day 1590 to 1772 for Ukraine subjects with extended study duration; Week 288: \geq Day 1926 (this applies for Ukraine subjects with extended study duration due to regional crisis) Note: as planned pregnancy visits are considered scheduled MRIs for analysis, they are also re-mapped using the same rules.

CONFIDENTIAL – FOIA Exemptions Apply in U.S.

^{*} These analysis windows applied for Laboratory (LB) assessments only, as described

^{**} This applied for subjects not impacted by regional crisis

^{***} This applied for Ukraine subjects with extended treatment period and additional visits

MSFC and SDMT: For premature EOT visits which occurred before day 245, the remapping rules follow the same in Table 7. For premature EOT visits and the EOT visits from patients who switched to commercial ponesimod, the remapping of EOT visits follows the same rule as in MRI and C-SSRS.

SF-36: For SF-36 questionnaires collected via an electronic device visit windowing is applied as a general process. To ensure a more precise visit labels, questionnaires based on dates will be assigned to the visits as following. If multiple questionnaires are available, the one closest to target is selected. The visit windowing will also be applied to premature EOT assessments.

```
Week 24 -- Target: Day 169; Range: Day 1 to Day 252;
Week 48 -- Target: Day 337, Range: Day 253 to Day 504;
Week 96 -- Target: Day 673, Range: Day 505 to Day 840;
Week 144 -- Target: Day 1009, Range: Day 841 to Day 1176;
Week 192 -- Target: Day 1345, Range: Day 1177 to Day 1512;
Week 240 -- Target: Day 1681, Range: ≥ Day 1513 for subjects who are not impacted by extended study duration, or Day 1513 to 1848 for Ukraine subjects with extended study duration;
```

Week 288 -- Target: Day 2017, Range: ≥ Day 1849 (this applies for Ukraine subjects with extended study duration due to regional crisis).

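### For non-laboratory data, Table 7 cuts Week 4 from Week 12 at Day 70/71 instead of the midpoint, Day 57, so premature-EOT blood pressure, EDSS and SDMT values from Days 58–70 cannot fill Week 12

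*SAP*

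**What the plan says.** Section 5.1.10 of the SAP lets a premature-EOT result stand in for a missing scheduled result. The condition is that "it can be replaced with a result from a premature EOT visit available in the respective visit window", with the windows set out in Table 7. A result can therefore fill only the visit in whose window its day falls.

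For data other than laboratory tests, the two rows at issue, the first beginning "Week 4 (Except LB", give nominal day, lower limit and upper limit as follows:

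- "Week 4 (Except LB) 29 23 70"
- "Week 12 (Except LB) 85 71 126"

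Laboratory data have their own rows for this period, among them "Week 8* (For LB only) 57 43 70".

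Section 5.1.10 also gives MRI, C-SSRS and SF-36 separate windows. MSFC and SDMT follow Table 7 for premature-EOT visits before Day 245. Section 5.1.4 says that premature-EOT visits are summarised within a scheduled visit using these windows, and it lists Extension Week 12 as a row in the by-visit tables of both analysis periods. The SAP states no midpoint rule for Table 7 in words, and it does not explain the Week 4/Week 12 cut.

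**The concern.** The Week 4 window reaches 6 days before its target and 41 days after it, although the next non-laboratory visit is only 56 days later. An EOT visit on Day 70 is 41 days from Week 4 and 15 days from Week 12, yet it is assigned to Week 4.

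The consequence depends on what is scheduled when (SAP Table 12):

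- **Blood pressure** is scheduled at both visits. The Week 4 value normally exists already, so an EOT value from Days 58–70 usually fills neither row.
- **EDSS and SDMT** are scheduled at Week 12 but not at Week 4. Their EOT values are directed to a visit where no such assessment is planned, and Week 12 stays empty for that subject.

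At stake is the content of the Week 12 row, and of the matching point in the mean-change plots, for these three parameters.

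**Working it through.** **Inputs.** Nominal days and limits from Table 7 (section 5.1.10); assessment schedule from Table 12 (section 6.12) and, for DLco, section 5.4.3.4.1; 877 subjects enrolled (section 3).

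**Step 1: how Table 7 places its boundaries.** For each adjacent pair, midpoint = (nominal day of earlier visit + nominal day of later visit)/2, compared with the stated upper limit of the earlier visit.

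| Data | Pair | Nominal days | Midpoint | Stated upper limit | Upper limit − midpoint |
|---|---|---|---|---|---|
| All | Week 2/4 | 15, 29 | 22 | 22 | 0 |
| **Non-lab** | **Week 4/12** | **29, 85** | **57** | **70** | **+13** |
| Non-lab | Week 12/24 | 85, 169 | 127 | 126 | −1 |
| All | Week 24/36 | 169, 253 | 211 | 210 | −1 |
| All | Week 276/288 | 1933, 2017 | 1975 | 1974 | −1 |
| Lab | Week 4/8 | 29, 57 | 43 | 42 | −1 |
| Lab | Week 8/12 | 57, 85 | 71 | 70 | −1 |
| Lab | Week 12/16 | 85, 113 | 99 | 98 | −1 |
| Lab | Week 16/20 | 113, 141 | 127 | 126 | −1 |
| Lab | Week 20/24 | 141, 169 | 155 | 154 | −1 |

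The pairs between Week 36 and Week 276 also give −1. Of 25 non-laboratory pairs, 24 are cut at the midpoint or one day before it. So are all 7 laboratory pairs from Week 2 to Week 36. Week 4/12 for non-laboratory data is the only exception. The SF-36 windows in the same section are also cut at midpoints; for example, (169 + 337)/2 = 253 is the first day of the Week 48 window.

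**Step 2: which days are affected.** Distance to Week 4 = day − 29; distance to Week 12 = 85 − day.

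| EOT visit day | To Week 4 | To Week 12 | Assigned by Table 7 |
|---|---|---|---|
| 56 | 27 | 29 | Week 4 |
| 57 | 28 | 28 | Week 4 |
| 58 | 29 | 27 | Week 4 |
| 64 | 35 | 21 | Week 4 |
| 70 | 41 | 15 | Week 4 |

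Thirteen days (58–70) are strictly nearer Week 12. Day 57 is a tie, and the table's prevailing convention gives the midpoint day to the later visit.

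**Step 3: where 70 could come from.** It equals 29 + 41, and 41 days is the reach that suits visits 84 days apart. It is also the end of the laboratory-only Week 8 window. The SAP does not say which applies, if either, and the point does not depend on it.

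**Step 4: which parameters are affected.**

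| Parameter | Week 4 | Week 12 | Effect of the 70/71 cut |
|---|---|---|---|
| Blood pressure | scheduled | scheduled | Cannot fill Week 12; Week 4 usually already filled |
| EDSS, SDMT | not scheduled | scheduled | Cannot fill Week 12 |
| Spirometry, DLco | scheduled | not scheduled | Can fill a missing Week 4 |

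**Step 5: size.** The SAP gives no count of EOT visits on these days. As an illustration only, assume that 2–5% of the 877 have a premature-EOT visit in the first 84 days, evenly spread. Over the 13 days this gives 877 × 0.02 × 13/84 = 2.7 to 877 × 0.05 × 13/84 = 6.8 subjects. Including Day 57, it is 877 × 0.02 × 14/84 = 2.9 to 877 × 0.05 × 14/84 = 7.3.

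**The case against.** The strongest reply is that no written rule is broken. Table 7 states no midpoint rule, its windows are contiguous and programmable, and another construction fits. Each early non-laboratory window is the union of two laboratory windows: 23–70 is laboratory Weeks 4 and 8, 71–126 is Weeks 12 and 16, and 127–210 is Weeks 20 and 24. This stands as a possible origin of the number. It does not justify the cut, because for the other two windows the union also ends one day before the midpoint, and only at Week 4/12 does it send results to the more distant visit.

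A second objection stands in full. Moving the cut for all non-laboratory data would send spirometry and DLco values from Days 57–70 to Week 12, where neither test is planned. That would repeat for pulmonary function the fault described here for EDSS and SDMT.

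A third limits the consequence. A reader might infer that these results are lost. They are not:

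- They appear in the Extension EOT row of the by-visit tables (section 5.1.4).
- Blood pressure abnormality incidence counts any treatment-emergent result, whatever its visit mapping (section 5.4.3.2.2).
- CDA is derived from all valid EDSS assessments by date (section 5.3.1.3.1).
- Section 5.1.4 looks first at the recorded visit label and then at a second, corresponding-visit label. An EOT visit already labelled as Week 12 would be used there before any remapping.

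Finally, the day that counts is that of the EOT visit, which may be up to 14 days after the last dose (section 1.2.3.1), not the day treatment stopped.

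**Conclusion.** The point holds in a narrow form. The Week 4/Week 12 cut for non-laboratory data is the one boundary in Table 7 that departs from the table's own pattern, and no reason is given. Applied as written, it keeps premature-EOT blood pressure, EDSS and SDMT values from Days 58–70 out of Week 12, the nearer visit. That the pattern is a midpoint rule is inferred from the other rows, not from a written statement.

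The effect is minor. It touches only descriptive by-visit output in a study without hypotheses (section 2). It probably concerns a handful of subjects; the 3–7 in the illustration rests wholly on assumed early stopping.

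A reader might also infer that the Week 12 row is biased toward subjects who tolerated treatment. The SAP does not support that: it gives no reasons for stopping in this interval. Subjects with an EOT visit before Day 57 stay out of Week 12 under either cut, so moving it would leave most of any such selection in place.

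**What to change.** In Table 7, for the parameters scheduled at Week 12 (blood pressure, EDSS and SDMT), set Week 4 (Except LB) to Days 23–56 and Week 12 (Except LB) to Days 57–126. This follows the table's prevailing convention that the midpoint day goes to the later visit. For spirometry and DLco, which are scheduled at Week 4 and not at Week 12, keep the present Week 4 limits of Days 23–70.

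The cost is one extra parameter-specific row in Table 7 and the matching programme line.
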